3.8.8.2. Coagulation

Blood draws for coagulation will include:

• Prothrombin time (PT), international normalized ratio (INR), activated partial thromboplastin (aPTT).

3.8.8.3. Chemistry

Blood draws for chemistry will be performed per the Schedule of Assessments (Table 1). Analysis will vary based on visit day as follows:

• Full serum chemistry - Baseline (Day 1) and EOS (Day 540)

Aspartate aminotransferase (AST), alanine aminotransferase (ALT), alkaline phosphatase (ALP), gamma glutamyl transferase (GGT), total bilirubin (TBIL), direct and indirect bilirubin, creatine phosphokinase (CPK), lactate, bicarbonate, uric acid, creatinine, blood urea nitrogen (BUN), estimated glomerular filtration rate (eGFR), sodium, potassium,

calcium, inorganic phosphate, chloride, albumin, total protein, glucose (fasting), glycated hemoglobin A1C (HbA1c), and tryptase (as required).

• Limited serum chemistry - Screening, Days 90, 150, 270, 330, 450 and 510 ONLY: AST, ALT, ALP, GGT, TBIL, CPK, creatinine, eGFR, fasting glucose, HbA1c (not at Day 150, 330, and 510) and tryptase (as required).

3.8.8.4. Inflammatory markers (IL6, IFN-γ, and TNF-α, hsCRP)

The hsCRP is performed routinely for safety throughout the study and is part of the central laboratory draws.

Tryptase and other inflammatory markers such as interleukin 6 (IL6), interferon-gamma (IFN- γ) and tumor necrosis factor-alpha (TNF- α) may be performed from centrally stored sample aliquots at a later date, as required. Should a subject develop anaphylaxis on days when inclisiran is injected, the investigator will need to collect a blood sample for tryptase within 30 minutes of the onset of anaphylaxis (or as soon as logically possible).

3.8.8.5. Urinalysis

Urinalysis will be performed at the time points defined in the Schedule of Assessments (Table 1) and evaluated by dipstick analyses at the investigational site (a standardized dipstick test will be supplied by the Central Laboratory). Urinalysis will be performed from a sample of mid-stream urine. In case of abnormal results, microscopy and other assessments will be performed at the local laboratory and the abnormality recorded as an AE.

The following parameters will be assessed:

• Nitrite, protein, glucose, ketone, urobilinogen, bilirubin, red blood cells/erythrocytes, white blood cells/leukocytes, pH, urine sediment (microscopic examination will be only performed in the event of abnormalities).

3.8.8.6. Urine Pregnancy

Urine pregnancy testing will be performed locally at the visits specified in the Schedule of Assessments (Table 1), using the supplies provided by the Central Laboratory.

3.8.8.7. Anti-drug Antibodies

A serum sample for analysis of the induction of antibodies will be collected at the time points in the Schedule of Assessments (Table 1). Collection will be prior to and 4 hours after first investigational product administration (injection) and then as per the Schedule of Assessments. As presented in Section 3, serum samples for analysis are collected at every visit but assessment of ADA will only occur for samples collected at the following visits: Randomization (prior to injection), Day 30, Day 150, Day 330, and Day 510. Samples will be stored for assessment (if needed) for samples collected at the following visits: Randomization (after injection), Day 90, Day 270, Day 450, and the End of Study Visit.

3.8.9. Stored samples

The central laboratory will take aliquots of serum and plasma samples from the received routine blood sampling noted above and will store these as frozen samples to permit future analysis of

the effect of inclisiran on the expression of these exploratory biomarkers. Analyses may include markers of CV risk (eg, hsCRP, IL6, P-selectin, Lp-PLA2, adiponectin). Biological samples for biomarker research will be retained on behalf of the Sponsor for a maximum of 1 year following the last subject's last visit in the study. Details regarding the collection, processing, storage, and shipping will be in the Study Laboratory Manual.

3.9. Assessment of Efficacy

Subjects will be in a fasted state for all efficacy laboratory assessments of lipids/lipoproteins/biomarkers. Specimens will be obtained at the time points in the Schedule of Assessments (Table 1). Pharmacodynamic parameters to be assessed will include:

• Total cholesterol (TC), triglycerides, LDL-C, HDL-C, non-HDL-C, VLDL-C, Apo-A1, ApoB, lipoprotein (a) [Lp(a)], hsCRP, and PCSK9.

LDL-C using ultracentrifugation will be done additionally at baseline and at Day 510.

Calculated LDL-C will use the Friedewald calculation, as the Friedewald equation (LDL-C = TC - HDL-C - TG/5) is typically used in clinical practice.

Blood samples for determination of LDL-C concentrations will be collected at the time points in the Schedule of Assessments (Table 1). Details regarding the collection, processing, shipping, and storage of the samples will be provided in a Laboratory Manual.

Additional aliquots of plasma and serum will be collected at each time point and stored for additional analyses, including future analysis of biomarkers of CV risk. Plasma samples will be analyzed using a validated enzyme linked immunosorbent assay to determine PCSK9 protein concentration. Full details of the analytical methods used will be described in a separate bioanalytical report.

3.10. Assessment of Pharmacodynamics

Assessment of lipids/lipoproteins as discussed in Section 3.9 will cover pharmacodynamics.

3.11. Assessment of Pharmacogenetics

All subjects will be invited to consent to pharmacogenetic analyses, unless underlying causal mutations of HeFH are well documented by a validated specialized laboratory.

A blood sample will be collected, preferably during screening, only from subjects who sign a separate consent for pharmacogenetics. Samples will be processed as described in the Laboratory Manual and stored. Genetic assessment will be performed by an accredited laboratory. This assessment will determine if there is a different response for LDL-C lowering based on the type of mutation(s).

4. ADVERSE EVENTS

This section will describe how the adverse events will be collected per protocol; analysis methods will be described in Section 6.4.8.1.

4.1. Adverse Event

Any untoward medical occurrence in a patient or clinical trial subject administered a medicinal product and which does not necessarily have a causal relationship with this treatment. An adverse event can therefore be any unfavorable and unintended sign (eg, an abnormal laboratory finding), symptom, or disease temporally associated with the use of a medicinal product, whether or not considered related to the medicinal product.

4.2. AE Severity

The severity of AEs will be assessed by the Investigator using the 3-point scale below:

- 1 = Mild: Discomfort noticed, but no disruption to daily activity.
- 2 = Moderate: Discomfort sufficient to reduce or affect normal daily activity.
- 3 = Severe: Inability to work or perform normal daily activity.

4.3. Study Drug Causality

The relationship between the AE and the investigational product will be assessed by using a binary assessment. The investigator should determine whether there is a 'Reasonable possibility' or 'No reasonable possibility' that the investigational product caused the event based on the definitions below.

Reasonable possibility - There is a reasonable possibility that the administration of the investigational product caused the AE. There is evidence to suggest a causal relationship between the investigational product and the AE.

No reasonable possibility - There is no reasonable possibility that the administration of the investigational product caused the AE. There is no temporal relationship between the investigational product and event onset, or an alternative etiology has been established.

4.4. Serious Adverse Event

Any untoward medical occurrence that at any dose:

- Results in death,
- Is life-threatening, i.e., the subject was, in the opinion of the investigator, at immediate risk of death from the event as it occurred (it does not include an event that, had it occurred in a more severe form, might have caused death),
- Results in a significant, persistent or permanent change, impairment, damage or disruption in the subject's body function/structure, physical activities and/or quality of life.
- Requires in-subject hospitalization or prolongs hospitalization,

- Is a congenital anomaly/birth defect, or
- Is another medically significant event where medical and scientific judgement should be exercised in deciding whether other situations should be considered serious reactions, such as important medical events that might not be immediately life threatening or result in death or hospitalization but might jeopardize the patient or might require intervention to prevent one of the other outcomes listed above. Examples of such events are intensive treatment in an emergency room or at home for allergic bronchospasm, blood dyscrasias or convulsions that do not result in hospitalization or development of dependency or abuse. Any suspected transmission via a medicinal product of an infectious agent is also considered a serious adverse reaction.

A distinction should be drawn between serious and severe AEs. Severity is an estimate or measure of the intensity of an AE, while the criteria for serious AEs are indications of adverse subject outcomes for regulatory reporting purposes. A severe AE need not necessarily be considered serious and a serious AE need not be considered severe. For example, nausea that persists for several hours may be considered severe nausea, but not an SAE. On the other hand, a myocardial infarction (MI) that may be considered minor could be an SAE if it prolonged hospitalization.

4.5. Additional collection of safety data: Special Situations

4.5.1. Special Situations

Special Situations designated for this study include:

- Medication errors that fall into the following categories
 - o wrong investigational product
 - o wrong dose (including overdose, underdose, change in dosing regimen, strength, form concentration, amount)
 - o wrong route of administration
 - o wrong subject (i.e., not administered to the intended subject)
 - o accidental exposure
- Pregnancy/lactation exposures with or without any AEs related to the parent or child
- Suspected transmission via a medicinal product of an infectious agent
- Drug interactions

4.5.2. Other safety related information

Injection site reactions (ISR) including individual signs or symptoms at the injection site following investigational product administration should be recorded on specifically designed electronic case report form (eCRF) pages. Photographs of ISR, if they were obtained during the study visits, should be forwarded to the study inbox.

Other safety related information that should be reported as adverse events in accordance with the process described in Protocol Section 8.4 are:

- Abnormal neurological examination, e.g., peripheral sensory and motor evaluation, an assessment of gait, pain, position, strength and reflexes (Protocol Appendix D).
- Potential anaphylactic reactions assessed by Sampson criteria (Protocol Appendix E). If Sampson criteria are positive, confirm by elevation of tryptase in blood plasma measured within 30 minutes of symptoms.
- Hyperglycemia-related AEs:

Report 'New onset of diabetes' in subjects with no medical history of diabetes when:

- o HbA1c becomes ≥6.5% and/or
- o Two consecutive values of fasting plasma glucose that are ≥126 mg/dL
- If a new concomitant medication for control of plasma glucose is added, further information to assess for a diagnosis of new onset diabetes will be collected.

Report 'Worsening of the glycemic control' or 'diabetic complications' in subjects with a medical history of disease (HbA1c \geq 6.5% at baseline) when:

- O HbA1c increases from baseline > 0.5% and/or
- New concomitant medication or increase in dose of current antidiabetic therapy is initiated to improve the control of plasma glucose level.

5. MEASURES TO MINIMIZE/AVOID BIAS

5.1.1. Blinded Study

This study will employ a double-blind technique with a placebo control. Randomization via automated interactive response technology (IRT) will be used to assign a subject to blinded investigational product. In addition, investigational product will be dispensed and administered in a blinded syringe. Blinding will minimize bias based on subject selection, baseline characteristics, clinical endpoint and AE reporting.

6. STATISTICAL PLAN

6.1. Sample Size

The sample size calculation is performed with the assumption (which is based on the observed results from a Phase II study) that the difference in change from baseline between the active dose group and the placebo group for LDL-C will be no less than 30 mg/dL, with a standard deviation of 20 mg/dL.

Assuming about a 5% drop out rate, the sample size will be approximately 380 subjects that are evaluable for efficacy across the placebo and inclisiran dose groups. This sample size of at least 380 evaluable subjects, will provide more than 90% power to detect a 30% reduction of LDL-C levels in the inclisiran group compared to the placebo group at one-sided significance level of 0.025. Due to faster than expected enrollment, actual enrollment was 482 subjects. This increased sample size will contribute additional safety data and not appreciably affect power calculations.

6.2. Randomization

Subjects will be screened and approximately 400 eligible subjects will be randomized by the IRT system: 200 subjects will be randomized to inclisiran sodium 300 mg and 200 subjects randomized to placebo. Due to faster than expected enrollment, actual enrollment was 482 subjects. Treatment allocation will be stratified by country and by current use of statins or other lipid-modifying therapies. Each subject will receive four subcutaneous (SC) injections of blinded inclisiran or placebo on Day 1, Day 90, Day 270, and Day 450.

6.3. General Statistical Considerations and Definitions

6.3.1. General Statistical Methods

All study-collected data will be summarized by treatment group using descriptive statistics, graphs, and/or raw data listings. Categorical variables will be summarized using counts and percentages. Percentages are based on the number of subjects in the analysis set for whom there are non-missing data, unless otherwise specified. Continuous variables, including changes from Day 1, will be summarized using descriptive statistics (n, mean, standard deviation [SD], median and interquartile range [first and third quartiles], minimum and maximum).

All p-values will be two-sided. All p-values will be rounded to three decimal places using the following algorithm. If the fourth digit of the p-value is less than or equal to 4, the p-value will be rounded down. If the fourth digit of the p-value is greater than or equal to 5, the p-value will be rounded up. All p-values rounded to 0.000 will be presented as '<0.001' and p-values that round to 1.000 will be presented as '1.000'.

Absolute change and percent change from baseline will be calculated as follows:

- Absolute Change = Value at Day X Baseline value.
- Percent Change = (Absolute Change/Baseline value)*100%.

6.3.2. Analysis Populations

The following populations will be used for data analyses and/or presentation.

6.3.2.1. Intent-to-Treat (ITT) Population

All subjects randomized into the study will comprise the intent-to-treat (ITT) population. Treatment classification will be based on the randomized treatment. The ITT population will be used for analysis of the primary and secondary endpoints.

6.3.2.2. Full Analysis Set (FAS)

All subjects who are randomized into the study, take any study medication and have at least one post treatment lipid data measured will comprise the full analysis set (FAS) population. Treatment classification will be based on the randomized treatment.

6.3.2.3. Modified Intent-to-Treat (mITT) Population

All randomized subjects who receive at least one dose of investigational product and have both the baseline and the Day 510 follow-up LDL-C assessment will comprise the modified intent-to-treat (mITT) population. Treatment classification will be based on the randomized treatment.

6.3.2.4. Safety Population

All subjects who received at least one dose of investigational product will comprise the safety population. Treatment classification will be based on the actual treatment received. A subject who receives any amount of inclisiran throughout the study will be analyzed within the inclisiran treatment group for the safety analyses. This will be primary population for the safety analyses.

6.3.3. Analysis Windows and Baseline

The analysis windows around each visit day are provided in Table 2: below.

Table 2: Analysis Windows for Each Scheduled Visit

Scheduled Visit	Analysis Window	
	From To	
Baseline		Before randomization/First Study Treatment
Day 30	Day 1	Day 60
Day 90	Day 61	Day 120
Day 150	Day 121	Day 210
Day 270	Day 211	Day 300
Day 330	Day 301	Day 390
Day 450	Day 391	Day 480
Day 510	Day 481	Day 525

Day 540 Day 526	No upper limit
-----------------	----------------

Data collected at scheduled or unscheduled visits will be used in the analysis if they fall into an analysis window for a scheduled visit. If more than one visit (scheduled or unscheduled) is made within the window specified above for any scheduled visit, the non-missing assessment closest to the scheduled visit day will be used in the analysis for that visit. However, all data will be included in the subject data listings.

Unless otherwise specified, data collected from assessments that occur more than once prior to initiation of investigational product administration, the latest assessment will be considered the "Baseline" evaluation for analysis.

6.3.4. Missing data handling

6.3.4.1 Efficacy

The sponsor will diligently follow up with each subject during the study through Day 540 ± 14 days on all efficacy laboratory assessments of lipids/lipoproteins/biomarkers to keep missing data to a minimum regardless of whether the subject is on study treatment, uses ancillary therapies, experiences an adverse event, or adheres to the protocol (these data points are referred to as retrieved data). However, if missing data, defined as data not available from either scheduled (within the protocol defined visit window) or unscheduled visits, occurs for the primary or any of key secondary efficacy endpoints then that data will be imputed.

The primary method to impute missing data for the first co-primary efficacy endpoint (percentage change in LDL-C from baseline to Day 510) will be a multiple imputation washout model. The washout model will be performed on actual values, change and percentage change values are calculated after the imputation. All retrieved data for subjects who dropped out from study treatment are considered as non-missing data and will be utilized in all analyses. See Appendix 2 for full details of the multiple imputation washout model.

In addition, sensitivity analyses using MMRM without multiple imputation and a control-based pattern mixture model (PMM, see details in Appendix 3) will be performed on the co-primary and key secondary efficacy endpoints to assess the impact of missing values. Note that the control-based PMM will be the primary method for imputing data for the second co-primary efficacy endpoint (time adjusted percentage change in LDL-C from baseline after Day 90 and up to Day 540).

Unless otherwise specified, missing data for all parameters not listed in the primary and key secondary endpoints will not be imputed and will be excluded from the associated analysis.

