10.3.4. Missing Data Handling

Primary and key secondary efficacy endpoints will have missing data imputed using multiple imputation techniques (a primary method and sensitivity/exploratory methods). The primary imputation method will utilize a washout model for subjects in the inclisiran arm where it will be assumed that early terminating inclisiran sodium 300 mg subjects have missing data after their last observed assessment (monotone missing data) return to baseline values. The baseline values will be randomly sampled from a population estimated using baseline data from all subjects. One sensitivity technique includes control-based pattern mixture models which utilize placebo data for monotone missing inclisiran sodium 300 mg treatment data. Additional sensitivity data imputation techniques will be utilized. Retrieved data will be

utilized in all analyses where possible. Full details, including how intermittent missing data and missing placebo data will be handled, will be provided in the SAP.

Unless otherwise specified, other missing data will not be imputed.

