6.4.6.2. Secondary Efficacy Endpoints

The secondary efficacy endpoints will not be tested if either one of the co-primary efficacy endpoints' null hypothesis fails to be rejected.

The key secondary endpoints of this study are:

- Absolute change in LDL-C from baseline to Day 510.
- Time adjusted absolute change in LDL-C from baseline after Day 90 and up to Day 540.
- Percentage change from baseline to Day 510 in PCSK9, total cholesterol, ApoB, and non-HDL-C.

The Hochberg procedure [Hochberg, 1988] will be applied to control the family-wise type I error rate at a two-sided significance level of alpha=0.05 for the key secondary endpoints.

Missing values will be imputed using the control-based PMM (see Appendix 2 for more details) on LDL-C, PCSK9, total cholesterol, ApoB, and non-HDL-C, absolute change or percent change from baseline will be calculated based on imputed data before any analysis is performed.

The absolute change in LDL-C from baseline to Day 510 and percentage change from baseline to Day 510 in PCSK9, total cholesterol, ApoB, and non-HDL-C will be analyzed using a MMRM with covariates as specified in Appendix 1 and Appendix 3. Time adjusted absolute change in LDL-C from baseline after Day 90 and up to Day 540 will be analyzed similarly to that of time adjusted percentage change in LDL-C from baseline after Day 90 and up to Day 540.

MMRM without multiple imputation (see Appendix 1) will be used as sensitivity analyses for the key secondary endpoints.

The other secondary endpoints of this study are:

- Maximum percentage change in LDL-C. This is calculated by finding the smallest LDL-C value across all post baseline visits for each individual subject. This value will be used to compare with each subject's baseline value and calculate the percent change from baseline to the lowest LDL-C value.
- Absolute change from baseline to Day 510 in PCSK9, total cholesterol, ApoB and non-HDL-C.

- Absolute change and percentage change in LDL-C from baseline to each assessment time up to Day 540.
- Individual responsiveness defined as the number of subjects reaching on treatment LDL C levels of <25 mg/dL, <50 mg/dL, <70 mg/dL, and <100 mg/dL at Day 510.
- Proportion of subjects in each group with greater or equal to 50% LDL-C reduction from baseline.
- Absolute change and percentage change in other lipids, lipoproteins, apolipoproteins, and PCSK9 from baseline at each subsequent visit to Day 540.

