- Proportion of subjects in each group who attain global lipid targets for their level of ASCVD risk.

The two-sided 95% confidence interval for least squares means will be provided for continuous variables at a single point using an analysis of covariance model or using MMRM methods for variables measured over time (see Appendix 1 for more details). The odds ratio and 95% confidence interval for the odds ratio will be provided for binary variables using logistic regression models. Nominal p-values will be provided when applicable.

Descriptive and graphical summaries by treatment group will also be presented.

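### Does leaving missing values out of the Day 510 LDL-C target-attainment analyses give inclisiran an unfair advantage?

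*SAP*

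**What the plan says.** **Endpoints.** SAP 6.4.6.2 lists three binary LDL-C or lipid endpoints among the other secondary endpoints:

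- Attainment of <25, <50, <70 and <100 mg/dL at Day 510, introduced as "Individual responsiveness defined as the number of subjects reaching on treatment" those levels.
- "Proportion of subjects in each group with greater or equal to 50% LDL-C reduction from baseline", with no visit named.
- Attainment of global lipid targets for the subject's risk level, also with no visit named.

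**Analysis.** The same section states: "The odds ratio and 95% confidence interval for the odds ratio will be provided for binary variables using logistic regression models". P-values are nominal.

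**Missing data.** Four rules bear on these endpoints:

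- SAP 6.3.4.1 starts imputation when missing data "occurs for the primary or any of key secondary efficacy endpoints then that data will be imputed".
- The same section closes by saying that "missing data for all parameters not listed in the primary and key secondary endpoints will not be imputed and will be excluded".
- Protocol 10.3.4 gives the default: "Unless otherwise specified, other missing data will not be imputed".
- SAP 6.3.1 sets the denominator: "Percentages are based on the number of subjects in the analysis set for whom there are non-missing data, unless otherwise specified".

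**Co-primary 1.** SAP Appendix 2 (restated in Addendum 2.5) fills a missing inclisiran value at Day 510 from placebo data and baseline (step 4). The exception is a subject with all four doses and a Day 540 value, who is imputed as missing at random from the inclisiran arm (step 3). Missing placebo values are imputed as missing at random.

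**The concern.** The first sentence in SAP 6.3.4.1 is framed by endpoint and the closing one by parameter. Day 510 threshold attainment is not a primary or key secondary endpoint, but LDL-C is a parameter in several of them. Taken literally, neither sentence settles the case.

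If the missing subjects are dropped, they are treated implicitly like the inclisiran subjects who were observed. Co-primary 1 treats most kinds of missing inclisiran subject, for the same variable at the same visit, as if they were on placebo. Response rates and odds ratios printed beside the co-primary result would then rest on a more favourable assumption. A reader would see how many values are missing by visit (SAP 6.4.1), but not what they do to the odds ratio.

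The on-treatment qualifier adds to this. It could be read as removing values taken after a subject stopped the drug, whereas SAP 6.3.4.1 says: "All retrieved data for subjects who dropped out from study treatment are considered as non-missing data and will be utilized in all analyses".

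**Working it through.** **1. Which rule applies.** The SAP trigger covers only primary and key secondary endpoints, the Protocol default is no imputation elsewhere, and percentages use non-missing data. All three point to observed cases. The doubt rests on the single word *parameters* in the closing sentence of SAP 6.3.4.1.

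**2. Inputs.** The documents give no expected response rate and no Day 510 missing rate. The nearest figure is the design drop-out of about 5% in SAP 6.1 (400 × 0.95 = 380, as stated there). Drop-out is not the same as a missing Day 510 value, because retrieved values count and the analysis window runs from Day 481 to Day 525. Everything below is therefore an assumption shown as a range.

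**3. Formula.** Let r and p be the inclisiran and placebo response rates, m the share of inclisiran subjects with no Day 510 value, and s the share of those who fall under step 4.

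- Rate under the co-primary 1 rule: r(1 − ms) + pms
- Gap from the observed-case rate: ms(r − p)

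The gap is never negative while r exceeds p, and it cannot exceed m.

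**4. Results with every missing inclisiran value made placebo-like (s = 1).** Each cell gives the gap in percentage points and how much larger the observed-case odds ratio is.

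| r vs p | 2% missing | 5% missing | 10% missing |
|---|---|---|---|
| 5% vs 0.5% | 0.1; 2% | 0.2; 5% | 0.5; 10% |
| 40% vs 2% | 0.8; 3% | 1.9; 8% | 3.8; 17% |
| 60% vs 2% | 1.2; 5% | 2.9; 13% | 5.8; 27% |
| 80% vs 20% | 1.2; 8% | 3.0; 19% | 6.0; 41% |

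One cell in full, 60% vs 2% at 5%: 0.60 × 0.95 + 0.02 × 0.05 = 0.571. The gap is 60.0 − 57.1 = 2.9 points. The odds are 0.60/0.40 = 1.500 and 0.571/0.429 = 1.331, a ratio of 1.127.

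If half of the missing subjects fall under step 3 (s = 0.5), the 5% figures become 1.5 points and 6% (60% vs 2%), and 1.5 points and 10% (80% vs 20%).

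**5. Check by simulation.** Assumptions: 241 per arm, lognormal baseline (mean 150, SD 50 mg/dL before truncation at 100), mean change −50% vs 0%, SD 20 points, 5% missing, s = 1, 400 replicates. The treatment difference shrinks by 0.3, 1.1, 2.2 and 3.2 points at <25, <50, <70 and <100 mg/dL, and by 2.5 points for a 50% reduction. This agrees with the formula.

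**6. Scale.** Take 482 subjects split equally (an assumption) and 5% missing, so 229 per arm. The 95% confidence interval of the odds ratio then spans a factor of exp(1.96 × SE) each way: 2.62 at 60% vs 2% and 1.58 at 80% vs 20%. The shifts at 5% missing are factors of 1.13 and 1.19.

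**7. The other possible denominator.** The threshold endpoint is worded as a count, and SAP 6.3.2.1 assigns secondary endpoints to the ITT population. Counted over all randomised subjects, with equal missingness in both arms, the difference is r(1 − m) − p(1 − m) = (r − p)(1 − m). The washout difference at s = 1 is r − m(r − p) − p, which is the same. At 60% vs 2% and 5% missing, both equal 0.58 × 0.95 = 55.1 points. SAP 6.3.1 argues against this denominator, but if it were used the gap in points would vanish.

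**The case for a change.** The strongest case for a change is consistency at low cost. The washout model imputes actual LDL-C values, so 100 completed Day 510 datasets already exist. Thresholds could be derived in each, a logistic model fitted, and the log odds ratios pooled by Rubin's rules. The direction of the gap is known in advance and favours the test drug.

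The direction and the arithmetic stand. The call for a change does not, for four reasons.

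- **The washout rule is a cautious convention, not a benchmark of truth.** Protocol 1.2.2.2 reports an effect still present 210 days after one dose. A subject dosed at Day 450 who then misses Day 510 and Day 540 is made placebo-like 60 days after an injection. A gap from that rule is not evidence of bias.
- **The SAP does not apply one rule to Day 510 LDL-C.** Absolute change to Day 510 (key secondary) uses the control-based model of Appendix 3 with MMRM. Its sensitivity analysis uses MMRM without imputation. Continuous other secondary endpoints measured over time use MMRM. Appendix 3 also borrows from placebo for subjects who left, so this is only partial support, but analysing observed data suits the lowest tier.
- **A bound is available from planned output.** Descriptive summaries of LDL-C by visit carry n by arm. With these and the observed response rates, the formula at s = 1 gives the largest shift by hand.
- **A new rule would be post hoc.** The SAP Addendum introduction dates its changes after unblinding, so further imputation now would carry no prespecified weight.

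The definitional gaps are real. SAP 6.3.4.1 settles the qualifier in practice, because retrieved values are to be used in all analyses. For the endpoints with no visit, Day 510 is the natural choice, since the threshold endpoint beside them and co-primary 1 use it; a by-visit table would also serve.

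**Conclusion.** No change follows. The documents, read together, give an observed-case analysis for the binary other secondary endpoints. Against the co-primary 1 convention, this raises the inclisiran response rate by about 0.2 to 3.0 points and the odds ratio by 5% to 19% at an assumed 5% missing. At 10% missing with every missing subject made placebo-like, the upper end of the range examined is 6.0 points and 41%.

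These sizes rest on assumed response rates, an assumed missing share and equal arms, none of which the documents supply. They shrink if missing subjects had all four doses and a Day 540 value. At 5% missing, the shift lies well inside the confidence interval of the odds ratio in the two cases checked. The endpoints carry nominal p-values, are outside the Hochberg family, and leave every primary and key secondary conclusion untouched.

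The visit, the denominator and the reading of on-treatment are details that the analyst states in the table footnotes. Whether to add imputed responder rates as supportive output is a choice on which reasonable statisticians differ.
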